3.2 Drivers of unhealthy diets and obesity

Unhealthy food environments are the major drivers of obesity and related non-communicable diseases (NCDs) (7). In Australia and NZ, as in most high- and middle-income countries, food environments are dominated by highly accessible, relatively cheap, and heavily promoted processed foods that typically contain high levels of sodium, saturated fat and/or added sugar (7, 8). In both Australia and NZ, less than half the packaged food available in supermarkets is classified as healthy, (8-10) and ~75% of Australian dietary sodium comes from processed foods (11).

3.3 Policy response in Australia and New Zealand

Improving the healthiness of food environments requires a comprehensive societal response, including government policies and wide-scale action from the food industry (12, 13). In Australia and NZ, current government policy in this area relies heavily on voluntary company actions through flagship initiatives such as the HSR nutrition labelling scheme and the Australian Healthy Food Partnership (a collaboration between government, food companies, and community groups, with the current focus mainly on product reformulation) (14). Some food and beverage manufacturers and retailers have taken positive steps to address population nutrition and obesity-related issues through changes to product development, reducing promotion of ‘less healthy’ food to children, and improved nutrition labelling (15, 16). Despite this, our recent assessments of company policies and commitments related to nutrition found they are frequently non-specific and limited in scope, and the overall response from the food industry to date has been weak and insufficient to meaningfully address population nutrition issues in Australia and NZ (15, 16). These findings are consistent with evidence from other countries (such as in relation to the United Kingdom government’s Public Health Responsibility Deal) where voluntary action (and support for industry) has been limited and compliance with voluntary pledges has been poor (17).

While the Australian and NZ governments encourage food companies to support healthy food environments via their voluntary schemes, and some food companies have expressly stated their willingness to act (15, 16), there is currently very limited support and expertise in place to guide companies in their policy development and implementation. In Australia, organisations such as VicHealth and the Heart Foundation provide some support for product reformulation (with a current focus on sodium reduction), with these types of initiatives having proved generally successful in Australia and elsewhere in relation to their specific policy targets (18, 19). State governments in Australia also offer some support for food companies to provide healthier products, such as through the Victorian Department of Health and Human Services’ Healthy

Eating Advisory Service (HEAS) (20). However, these schemes are limited in their scope (currently focused mainly on guidance with assessment of the healthiness of products), their level of assistance available, and do not apply nationally. The level of support for food companies is similarly low in NZ with only the Heart Foundation offering assistance to the food industry to improve the nutritional quality of foods (21).

4. Rationale for the Present Study

In a recent project led by A/[name], we developed the novel BIA-Obesity (Business Impact Assessment – Obesity and population nutrition) tool and process for assessing food company policies and practices related to nutrition (22). The BIA-Obesity tool assesses key domains related to obesity prevention and improving population nutrition, including: i) overall corporate strategy related to nutrition; ii) product composition (reformulation of existing products and new product development); iii) product and brand promotion; iv) nutrition labelling; and v) product accessibility (including availability and affordability). BIA-Obesity involves extensive engagement with company representatives as part of the assessment process. The BIA-Obesity monitoring tool has now been applied in Australia (2018), NZ (2018), Canada (2019) and Malaysia (2019), with assessment underway in parts of Europe as part of the INFORMAS (International Network for Food and Obesity/Non-communicable Diseases Research, Monitoring and Action Support) initiative (23). Levels of company engagement with the BIA-Obesity initiative in Australia, NZ and Canada were high, with the majority of the included companies actively engaging in the process (22). Our evaluation of the BIA-Obesity initiative in Australia revealed that company representatives found the process extremely useful in generating internal advocacy for action, and in highlighting priority focus areas at the executive-level (24). In addition, the evaluation of BIA-Obesity indicated that companies are calling for expert support to design and implement best practice policies related to nutrition. For example, company representatives that participated in BIA-Obesity stated:

“When we want [nutrition-related] advice and different insights it’s very, very hard to get. It’s really hard to get because sometimes the best perspective to help you think about what you’re doing is a completely different perspective to the one [the company has]... A willingness [from the public health community] to provide input and advice... would be really helpful” – Company representative (external/public relations/affairs role)

“What would be interesting for you [public health researchers], I think, would be to go directly to some of the food companies at the bottom of the list [of food companies ranked by their nutrition-related policies] who don’t have the nutrition resources... maybe your role in some of those lower ranking companies is distinctly to generate action to improve their policies and practices” – Company representative

Moreover, in the last 18 months we have been approached by a range of food manufacturers (including Fonterra, Nestlé and Lion), supermarkets (including all major chains), and small retailers to provide our expertise regarding their nutrition policies on a consultancy basis. However, there is currently no evidence that such a model is effective. In addition, providing support to companies through consultancy would breach the conflict of interest guidelines of the Global Obesity Centre (GLOBE) at Deakin University (25). With an RCT funded from government sources, we can avoid financial conflict of interest and generate rigorous evidence of whether the process of offering expert advice and support can strengthen voluntary initiatives and have a meaningful impact from a population health perspective.

Advocacy is the process of influencing people and organisations to create change (26). Coupled with direct support for change, advocacy can potentially lead to improvements in corporate behaviours and industry practices that are currently misaligned with health (27). Our experience strongly suggests that many large corporations in the food industry are keen to shift their practices towards healthier policies and products, particularly in response to consumer opinion and a desire to maintain brand reputation. However, little evidence exists to describe the effects of advocacy and support programmes on food company behaviour (28).

Members of the project team, including [name] and [name], previously conducted a pilot advocacy intervention to reduce the sodium content of processed foods in Australia (2013-2015) (29). Twenty-three companies in the control group received no specific intervention and 22 companies in the intervention group received an advocacy programme based on an established theory of change model (COM-B) (30). Evaluation of the pilot programme identified no differences between the intervention and control groups in pre-defined interim measures, although the study had power to detect only large effects on food composition measures (29). Further, the primary outcome was the sodium content of foods, when a composite measure of overall nutrient profile is arguably a more appropriate measure for a food reformulation initiative. This pilot work provided important insights into mechanisms for delivering an effective advocacy intervention involving food companies as well as the level of resources and time required. The learnings from the pilot study have directly informed the development of this proposal.

The proposed project seeks to evaluate the effects of providing tailored support for food companies to implement best practice policies for improving population nutrition. The intervention design will be based on a framework for advocacy developed by the World Health Organization (WHO) (26), other relevant literature and resources, and the research team's extensive experience evaluating industry initiatives and interventions. Targeted companies will be the largest food and beverage manufacturers and fast food chains in Australia and NZ. Accordingly, the project has exceptional potential to impact the food environments of almost all Australians and New Zealanders.

5. Study Objectives

The primary objective of this trial is to determine the effects on the nutrient profile (Health Star Rating) of food company product portfolios, of provision of tailored support to companies on their nutrition-related policies and practices (food composition, nutrition labelling, marketing to children, food accessibility), compared to food companies that are not offered the programme (the control). We hypothesise that the tailored support programme will be more effective than no intervention at 24 months' post-baseline.

6. Study Design

The study is a parallel, two-arm, cluster randomised controlled trial (RCT) with food companies as the unit of randomisation. Food companies will be randomised to receive either the intervention (a package of actions designed to support food companies to improve their nutrition-related policies and practices—described below) or no intervention (control).

6.1 Inclusion criteria

The following food and beverage companies will be eligible for inclusion in the trial:

- A company involved in the production of food and/or non-alcoholic beverages
- >\$10 million in annual retail sales revenue
- Holding Company or Head Office and manufacturing located in Australia or New Zealand.
 - In cases where a company has head offices in both Australia and New Zealand but manufacturing and/or nutrition-related policy decisions are made primarily in one country, the company will only be included in the primary decision-making country sample.
- Product portfolio of at least 10 products considered by the research team to be amenable to reformulation (defined as a product where composition may be altered to improve nutritional profile and therefore Health Star Rating)

6.2 Exclusion criteria

- Companies that manufacture chewing gum products, sports supplements, or infant formula *only*
- Companies currently engaged with the research team on similar interventions
- They are supermarkets or retailers/distributors/importers/wholesalers only
- Companies whose product nutrition information is not available in the Nutritrack or FoodSwitch databases and therefore nutritional profile and HSR is unable to be assessed.

6.3 Recruitment

Potentially eligible companies in Australia and New Zealand will be identified using the Euromonitor Passport Database (31). Packaged food and non-alcoholic beverage (soft drink) companies and Chained Consumer Food Service (fast food) will be considered separately. Companies in each of the two industry sectors will be ranked based on their 2019 category market share and sales revenue. Rankings will be conducted separately for Australia and New Zealand and potentially eligible companies will be initially identified.

We aim to recruit a total of 150 companies, which will be randomized to study intervention (n=100) or control (n=50) groups prior to commencement of the intervention. Control companies will not be contacted by the study team during the intervention phase. For companies allocated to the intervention group, contact details for representatives of the company will be obtained from a variety of sources including: i) existing networks of the research team and partner organisations; ii) relevant industry associations and forums; and iii) company websites and social media sites. Targeted company representatives will typically be in the role of nutritionist, regulatory affairs, or external affairs.

We estimate that only half of companies randomised to receive the intervention will participate in the intervention programme. As such, we will identify up to twice the required number of

eligible intervention companies and will approach all companies randomised to the intervention group, to invite them to participate.

Neither intervention nor control companies will be aware of the RCT design. When intervention companies are approached, we will not mention that this study is a RCT. Instead, these companies will simply be invited to participate in the intervention programme. The programme will consist of multiple elements delivered over the period of 12 months (see below). The framework for the study intervention will be the opportunity to engage in a tailored support programme to help improve company nutrition-related policies and practices.

6.4 Study intervention

- **Intervention group**

The intervention period will span 12 months and include a range of actions to engage with intervention companies and support them to improve their nutrition-related policies and practices. Targeted policy areas include product composition (policies and targets for reducing nutrients of concern with respect to reformulation of existing products and development of new products), nutrition labelling (adoption of HSR, voluntary labelling of added sugar and trans fats, and use of nutrient-content claims), marketing to children (policies and practices for reducing the exposure of children to unhealthy products and brands) and product accessibility (policies related to the availability and pricing of healthy versus unhealthy products).

Actions included as part of the intervention will be based on established behaviour change techniques (31) and the WHO framework for practical and successful advocacy, which includes seven key steps: (i) define the situation, (ii) establish goal and objectives, (iii) identify target audiences, (iv) develop key messages to influence target audiences, (v) develop and implement advocacy plan, (vi) engage media interest and (vii) monitor and evaluate (26). The strategies used to engage companies will build on our teams' engagement with companies as part of the BIA-Obesity initiative (22), and existing relevant relationships of our Australian partner organisations.

A core component of the intervention will be a tailored support programme. This will include company-specific reports on the nutrient profile of a company's product portfolio, their adoption of HSR, and their rankings compared to those of competitor companies (using data sourced from the Nutrtrack and FoodSwitch databases). Intervention companies will also be provided with detailed and specific advice on ways to improve their other nutrition-related policies and practices that will draw upon a detailed assessment of company policies and areas for improvement, and the provision of exemplars of both international and national good practice in each domain (e.g., case studies of successful product reformulation efforts). Intervention companies will receive relevant customer insight data and where appropriate, will be provided with information on existing networks, workshops, and support mechanisms of relevance to their industry sector in each country. All intervention materials will be developed in partnership with stakeholders with expertise in consumer campaigns and advocacy. The intervention will span 12 months, but study outcomes will be measured at 24 months to maximize the time available for companies to enact changes.

One of the opportunities presented to intervention companies as a reason to engage with the research team, will be input into the development of a nutrition-related awards/recognition programme. The details of the awards/recognition programme will be developed iteratively as part of the study. It is expected to consist of a list of pre-defined pledges that companies will be

encouraged to sign up to, with annual auditing and renewal of pledges and practices. It is envisaged that the awards/recognition programme will be sector-specific, based on best practice evidence from a public health perspective, and will have independent governance arrangements.

- **Control group**

The control group will not be contacted or offered the intervention during the trial. Generic intervention resources produced for the study, including guides, case studies and referral networks, will be made available to control companies at 24-months post baseline. In addition, an overview of intervention outcomes including ‘lessons learned’ will be offered to all intervention and control companies.

6.6 Blinding

Neither intervention nor control companies will be aware of the RCT design. Due to the nature of the intervention, food companies allocated to the intervention group will be aware of the programme, as will research staff who engage with the companies. Food companies allocated to the control group will not be contacted during the trial intervention period. Outcome assessments on the foods and beverages produced and sold by all trial food companies will be conducted independently using the Australasian Health Star Rating (HSR) nutrient profiling system, and information extracted from country-specific food product databases (New Zealand Nutritrack databases and Australian FoodSwitch database).

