6.9 Baseline assessments

Baseline assessments will be conducted for all randomised companies utilising publicly available, routinely collected data where possible, including:

- Relevant company demographics and information (company name, key brands, product categories, category market share, category sales revenue, head office location)
- Baseline product portfolio information (number of products, average nutrient content per 100g (energy, saturated fat, sodium, total sugar, fibre etc.), mean estimated HSR, % products displaying HSR)
- Company nutrition-related policies and commitments

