6.11 Secondary outcome measures

The following secondary outcome measures will also be collected and assessed:

- Nutrient profile (measured using the HSR system) of the foods and beverages produced and sold by participating food companies at 12-months post-baseline.
- Nutrient content (including sodium, sugar, and saturated fat) of the foods and beverages produced by the food companies at 12- and 24 months post-baseline. The nutrient data will be extracted from the New Zealand Nutritrack and Australian FoodSwitch databases.
- Display of HSR labels on packaged foods and beverages produced by the food companies at 24 months post-baseline.
- Company nutrition-related policies and commitments at 24-months post-baseline, measured using the validated BIA (Business Impact Assessment)-Obesity tool (22). Publicly available data related to company policies and commitments to improve population nutrition will be assessed at baseline. Surveys (control and intervention companies) will be used to collect data at 24 months post-baseline. Policy areas include product formulation, product labelling, marketing to children and accessibility (price and availability) of healthy and unhealthy food.
- Company engagement with the intervention and reported, mechanisms, enablers, and barriers to improving nutrition-related policies and practices will be measured via the process evaluation interviews and surveys. Data collection for intervention food companies will occur via survey at baseline and 24 months post-baseline. Control companies will receive a survey at 24 months post-baseline only. Representatives from selected intervention and control companies will be invited to participate in in-depth interviews at

24 months post-baseline. Key indicators will be change relative to baseline in company prioritization and motivation for change, and change mechanisms and resources.

- Information on resources used to develop the awards/recognition programme, implement the intervention, and those accrued by intervention companies will be collected using resource use questionnaires. Resource use data and the primary outcome estimate will be used to conduct a within-trial cost-effectiveness analysis and a modelled analysis incorporating the population health impact of the intervention.

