The FoodSwitch dataset contains nutrient information obtained directly from the NIP of all packaged food and beverage products available for sale from five large supermarket retailers in Sydney, Australia (Woolworths, Coles, Aldi, IGA and Harris Farm). Data are collected by trained personnel during the months of August to November each year. For each product, the product name, package size (g), and nutrient content per 100g/mL and per serve are recorded. Food and beverages are classified according to a hierarchal system to classify products into major categories (e.g., dairy), minor categories (e.g., milk), major subcategories (e.g., soy milk) and minor subcategories (flavoured soy milk) (36, 37).

7.3.3 *BIA-Obesity*

Assessment data relating to food company policies will be collected from publicly available information obtained from company websites and other online sources, or directly from company representatives (at follow-up only). Although individual participant information may be collected to facilitate communication and to arrange any phone calls or meetings as necessary, no additional identifying information will be collected throughout the process. Names of company representatives will not be released. In some cases, companies may request that commercial in confidence information that they provide to the research team be used only for the purposes of the study and scoring using the BIA-Obesity tool, but not for other purposes.

7.3.4 *Process evaluation*

For ease of consultation with colleagues and completion, surveys will be paper-based (fillable PDF) and emailed to company representatives to fill out via computer or legibly by hand. Each company will be assigned a unique study ID which will appear on the survey. Once completed, company representatives will be asked to (scan if completed by hand) and email the completed survey to the research team. Scanned email responses and survey will be saved on a secured restricted folder at The University of Auckland or Deakin University.

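### The BIA-Obesity policy score, a between-arm secondary outcome, has no stated masking or separation of scorers, although the research team also uses the tool to advise intervention companies

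*Protocol*

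**What the plan says.** Section 6.6 of the protocol deals with blinding. Companies do not know that the study is a randomised trial, but "food companies allocated to the intervention group will be aware of the programme, as will research staff who engage with the companies". The safeguard that follows is specific to products: "Outcome assessments on the foods and beverages produced and sold by all trial food companies will be conducted independently", by means of the HSR system and data extracted from Nutritrack and FoodSwitch.

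Section 6.11 lists a secondary outcome of another kind: "Company nutrition-related policies and commitments at 24-months post-baseline, measured using the validated BIA (Business Impact Assessment)-Obesity tool". Its sources are given there: "Publicly available data related to company policies and commitments to improve population nutrition will be assessed at baseline", and "Surveys (control and intervention companies) will be used to collect data at 24 months post-baseline". Section 7.2.2 tests primary and secondary efficacy outcomes between arms, with the baseline value of the outcome as a covariate.

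Section 7.3.3 describes the policy data. Material from companies goes to the research team, and a company may ask that it "be used only for the purposes of the study and scoring using the BIA-Obesity tool". No scorer is named.

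The same tool is part of the intervention. The schematic in section 2 has companies shown how they rate, using BIA-Obesity policy assessments among other data, and then supported to do better. Appendix 3 lists the BIA-Obesity criteria among the resources provided. Section 6.4 says that the policy advice draws on a "detailed assessment of company policies and areas for improvement".

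On timing, section 6.9 says "Baseline assessments will be conducted for all randomised companies", and its list includes policies and commitments. Section 7.4.3 describes baseline assessment specifically for control companies.

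**The concern.** HSR is calculated from label values, so knowing the arm gives an assessor little room to influence it. The BIA-Obesity score rates policies and commitments, and the protocol describes no comparable calculation for it. A scorer who knows the arm, or who has helped a company strengthen its policies against the same criteria, may read borderline evidence more generously at 24 months. If baseline scoring was also done with the arm known and with the aim of finding gaps, it may have been harsher for intervention companies. Both errors would push the comparison towards benefit.

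Using the same information sources in both arms does not cure this, because the problem lies with the scorer and not with the source. What is at stake is whether a difference in policy score can be read as an effect of the programme.

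**Working it through.** **Setting the sections side by side**

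| Question | Product outcomes | BIA-Obesity score |
|---|---|---|
| Compared between arms? | Yes (6.10, 6.11, 7.2.2) | Yes (6.11, 7.2.2) |
| Independent assessment stated? | Yes (6.6) | No |
| Scorer or masking stated? | Databases and HSR calculator (6.6, 6.10) | No; information goes to the research team (7.3.3) |
| Used within the intervention? | Yes, in company reports (6.4) | Yes (section 2, Appendix 3) |

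The safeguard in 6.6 covers HSR and, plausibly, nutrient content and HSR label display, since these are product measures. It cannot be read to cover company policies.

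**Timing**

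The 24-month score is certainly made after allocation. For baseline, 6.9 and 7.4.3 read most naturally as assessment of companies whose arm is already fixed. Table 1, however, puts baseline data collection and randomisation in one column without an order. Baseline scoring after allocation is therefore possible but not established.

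**Size, as an illustration**

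The protocol gives no SD, power figure or likely scoring bias for BIA-Obesity; its power statement (section 7.1) concerns HSR only. The bias below is therefore assumed.

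Inputs: 100 intervention and 50 control companies (section 7.1), a two-sided 5% test (section 7.2.2), one score per company, no true effect, no covariate adjustment.

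- SE = SD × √(1/100 + 1/50) = SD × √0.03 = 0.173 SD.
- For a scoring shift b in SD units, P(significant) = Φ(b/SE − 1.96) + Φ(−b/SE − 1.96).

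Sections 6.3 and 7.1 expect about half of the intervention companies to participate. If only those are scored generously, the shift for the whole arm is b/2.

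| Assumed bias per affected company | Whole arm affected: shift/SE | Nominal significance | Half affected: shift/SE | Nominal significance |
|---|---|---|---|---|
| 0.1 SD | 0.58 | 9% | 0.29 | 6% |
| 0.2 SD | 1.15 | 21% | 0.58 | 9% |
| 0.3 SD | 1.73 | 41% | 0.87 | 14% |

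If instead only half of each arm returned data (50 v 25, also assumed) and every scored intervention company were affected, SE = √(1/50 + 1/25) = 0.245 SD and the three rates would be about 7%, 13% and 23%.

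**Baseline adjustment**

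Write b24 and b0 for the scoring bias (intervention minus control) at 24 months and at baseline, and β for the slope on baseline. The adjusted estimate is then off by b24 − β × b0. With positive β, harsher baseline scoring of the intervention arm (b0 < 0) adds to the bias, while steady leniency at both times (b0 > 0) is partly removed. Adjustment can therefore make matters worse or better, and the protocol does not allow one to say which.

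**The case against.** The strongest reply is that the tool is described as validated, that three institutions share the study, and that 6.6 attributes knowledge of allocation only to staff who engage with companies. Scoring may well be done by others. This stands as far as it goes: the documents do not say that the people who advise a company also score it. But they do not separate the roles either. Section 4 describes BIA-Obesity as involving extensive contact with company representatives during assessment; if that is followed here, the scorers are among the staff whom 6.6 describes as aware. Validation of a tool does not mask the person using it.

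Four stronger readings are tempting and are not supported:

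- **Only HSR is protected.** The wording of 6.6 on foods and beverages plausibly extends to nutrient content and label display.
- **Control companies get only a desk assessment.** Sections 6.11 and 7.4.3 have both arms surveyed at 24 months, by a similar process.
- **Baseline scoring is known to be unmasked.** The phrase in 6.9 can define which companies are assessed rather than when. Table 1 shows engagement of intervention companies in a column before baseline and randomisation, but section 6.3 makes clear that the companies approached are those already randomised to the intervention. The column order does not settle when policies were scored.
- **The score is largely a matter of judgement.** The scoring rules are in a cited source that is not at hand, so how much judgement they leave is unknown.

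The figures can also be challenged, because a bias across all 100 companies is a severe assumption when half are expected to decline. That is why the half-affected case is shown beside it.

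**Conclusion.** The point holds as a gap in the protocol. One between-arm secondary outcome lies outside the only assessment safeguard in 6.6, while the research team uses the same tool in the intervention. As written, a difference in BIA-Obesity score at 24 months could not be separated from assessor bias. Exposure at 24 months is certain; at baseline it is possible.

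The size is unknown. Under the assumptions shown, the chance of a nominally significant result with no true effect rises from 5% to between about 6% and 41%, depending on the bias assumed and on whether half or all of the intervention arm is affected. These figures illustrate sensitivity and are not estimates.

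The primary HSR outcome is unaffected. Who scores an outcome, and whether they know the arm, is a matter of trial conduct that belongs in the protocol's blinding section, so a separate analysis plan would not be expected to supply it. The change is worth making, but the main conclusion of the trial does not depend on it.

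**What to change.** In sections 6.6 and 7.3.3, state that BIA-Obesity at 24 months is scored from a dossier that carries only a study ID, with allocation withheld, by existing team members who did not deliver the intervention to that company. One practical arrangement is for the Australian and New Zealand teams to score each other's dossiers.

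For baseline, either score before allocation is released or score in the same masked way from archived public documents dated at baseline. In both cases keep the outcome score separate from the feedback report given to intervention companies.

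The cost is protocol wording and some coordination to prepare and exchange dossiers. Masking will be imperfect where a document or survey reply mentions the programme. Where it is not feasible, the protocol and the trial report should say that this outcome was assessed unblinded.
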